13.3. Analysis Populations

The following 4 analysis populations are planned for this study:

- Intent-to-Treat (ITT): Includes all consented and randomized subjects. Regardless of any protocol deviations, analyses performed on the ITT set will be based on the randomized treatment assignment and all available data.
- Full Analysis Set (FAS): Includes all randomized subjects who have had at least 1 patch of double-blind study drug applied and who have a Baseline WOMAC pain score and at least 1 post-baseline assessment of the primary efficacy measure (WOMAC pain score). Evaluable subjects will be defined as those who meet the FAS definition. The FAS will be used as the primary set for analysis of efficacy endpoints based on randomized treatment assignment.
- Safety Analysis Set (SAF): Includes all subjects who have had at least 1 patch of Double-blind study drug applied and who have at least 1 post-dose safety measurement during the Double-blind Treatment Phase. In the unlikely event that errors may have occurred in treatment arm assignments, then analyses using the SAF will be based on treatment actually received. The SAF will be used for the analysis of dermal evaluations and safety endpoints.
- Pharmacokinetic Analysis Set (PAS): Includes all subjects who have received at least 1 dose of study drug during the Double-blind Treatment Phase and have at least 1 blood sample for PK assessment. Subjects may be excluded from the PAS set if they significantly violate inclusion or exclusion criteria, significantly violate the protocol in a way that may influence the PK analysis, if any unexpected error occurs during the study that may influence the PK analysis (e.g., early detachment of transdermal systems, apparent sample switching, etc.) or if their data are unavailable or incomplete. The PAS will be used for the analysis with model-based approach. Excluded cases will be documented together with the reason for exclusion.

Inclusion in the analysis populations will be determined prior to database lock.

If a subject is randomized incorrectly or is administered the incorrect study drug, analyses of the ITT population will be based on the assigned treatment whereas all other analyses will be based on the actual treatment.

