4.2. Interim Analysis and Data Monitoring

No interim analysis is currently planned. If an interim analysis is planned in the future, this will be amended in protocol and in the SAP text as applicable.

5. Analysis Populations

The following 4 analysis populations are planned for this study:

- **Intent-to-Treat (ITT):** Includes all consented and randomized subjects. Regardless of any protocol deviations, analyses performed on the ITT set will be based on the randomized treatment assignment and all available data.
- **Full Analysis Set (FAS):** Includes all randomized subjects who have had at least 1 patch of double-blind study drug applied and who have a Baseline WOMAC pain score and at least 1 post-Baseline assessment of the primary efficacy measure (WOMAC pain score). Evaluable subjects will be defined as those who meet the FAS definition. The FAS will be used as the primary set for analysis of efficacy endpoints based on treatment actually received.
- **Safety Analysis Set (SAF):** Includes all subjects who have had at least 1 patch of double-blind study drug applied and who have at least 1 post-dose safety measurement during the double-blind treatment phase. In the unlikely event that errors may have occurred in treatment arm assignments, then analyses using the SAF will be based on treatment actually received. The SAF will be used for the analysis of dermal evaluations and safety endpoints.
- **Pharmacokinetic Analysis Set (PAS):** Includes all subjects who have received at least 1 patch of double-blind active study drug applied and who have at least 1 blood sample for PK assessment. Subjects may be excluded from the PAS set if they significantly violate inclusion or exclusion criteria, significantly violate the protocol in a way that may influence the PK analysis, if any unexpected error occurs during the study that may influence the PK analysis (e.g., early detachment of transdermal systems, apparent sample switching, etc.) or if their data are unavailable or incomplete. Excluded cases will be documented together with the reason for exclusion. In the unlikely event that errors may have occurred in treatment arm assignments, then analyses using the PAS will be based on treatment actually received.

Inclusion in the analysis populations described above will be determined prior to database lock.

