7.1. Primary Efficacy Analysis

The estimand in the primary analysis for efficacy for each dose is the difference between treatments groups (each HP-5000 treatment group vs. placebo) in the change from Baseline to Week 4 in WOMAC pain score in all subjects as randomized, under the assumption that all randomized patients remain on their randomized treatment throughout the trial.

AD-ST-33.04 Effective date: 30-Jun-2017

Version 1.0 | Date 21-Oct-2019 | AD-PR-109.01 Effective date: 26-Jun-2017

Page 24 of 124

Statistical Analysis Plan,
 Sponsor Noven Pharmaceuticals, Inc.
 Protocol Number HP-5000-US-05
 [REDACTED]

The comparisons of interest are:

- HP-5000 [REDACTED] versus placebo
- HP-5000 [REDACTED] versus placebo

WOMAC scores obtained 24 hours after removal/detachment of the study medication or WOMAC scores obtained within 24 the subject used rescue medication will be excluded as outliers. Outliers will be defined *a priori* as (i) WOMAC scores obtained more than 24 hours after removal/detachment of double-blind study medication; or (ii) WOMAC scores obtained within 24 hours the subject used rescue medication.

The change from Baseline to Week 4 in the WOMAC pain score will be analyzed using a mixed model repeated measures (MMRM) analysis. The MMRM model will include change from baseline in WOMAC pain score as the repeated dependent variable, with treatment (HP-5000-[REDACTED], HP-5000-[REDACTED], and placebo), visit, treatment-by-visit interaction, and the baseline WOMAC pain score as covariates. The mean difference of change will be compared for each active treatment arm, and overall active against placebo. An unstructured covariance matrix will be assumed. If the unstructured matrix fails to converge, a series of other covariance structures will be tested (AR(1), Toeplitz, and Compound Symmetry). The covariance structure which converges with the lowest Akaike information criterion (AIC) score will be chosen and noted in the resulting table. The Kenward-Roger approximation for denominator degrees of freedom will be implemented, and the restricted maximum likelihood (REML) approach for estimation will be specified in the model code.

Below is example SAS code for conducting the MMRM analysis specified. Note, the macro wrapper used in different covariance structures is not shown below (specified with type option):

[figure not shown]
[figure not shown]
[figure not shown]
```
ods output lsmeans = lsmn1
      lsmestimates = lsmest1

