p-value (LS Mean = 0)	x.xxx	x.xxx	x.xxx	x.xxx
LS Mean Difference from Placebo (SE)	x.xx (x.xxx)	x.xx (x.xxx)	x.xx (x.xxx)	x.xx (x.xxx)
(95% CI for Mean Difference from Placebo)	(x.xx, x.xx)	(x.xx, x.xx)	(x.xx, x.xx)	(x.xx, x.xx)
p-value (LS Mean = Placebo LS Mean)	x.xxx	x.xxx	x.xxx	x.xxx

Note: Assigned/planned treatment groups are presented. CI = confidence interval, LS = least-squares, MMRM = repeated measures mixed model, SE = standard error, WOMAC = West Ontario and McMasters Universities Osteoarthritis Index. Treatment arms: HP-5000 [REDACTED] topical patch, HP-5000 [REDACTED] topical patch, and Placebo.

[1] Estimates are from a repeated measures mixed model with change from baseline as the dependent variable and subject as the random repeated factor. Terms for treatment, visit, treatment-by-visit, and baseline WOMAC Pain Score as covariates are included. The Kenward Roger approximation for denominator degrees of freedom is implemented and the restricted maximum likelihood (REML) approach for estimation is used. An unstructured covariance matrix converged.

SOURCE: Listings xx.x.x, xx.x.x

T:\Noven\HP-5000-US-05\...\xxxxxx.sas run on DDMMYY at HH:MM for data extracted on DDMMYY, on SAS v9.4

{Programming Note: If type=un fails to converge, follow SAP guidance and update footnote indicating which covariance structure is used.
 Repeat above layout for Week 2, and Week 4}

Statistical Analysis Plan,
 Sponsor Noven Pharmaceuticals, Inc.
 Protocol Number HP-5000-US-05
 [REDACTED]

Noven Pharmaceuticals, Inc.
 Protocol HP-5000-US-05

Page 1 of x
 FINAL

Table 14.2.1.4
 ANCOVA Analysis on Rank-Transformed WOMAC Pain Score by Study Visit
 Full Analysis Set

Visit/Category Statistics [1]	HP-5000-[REDACTED] (N=xx)	HP-5000-[REDACTED] (N=xx)	Overall HP-5000 (N=xx)	Placebo (N=xx)
Week 1 Change from Baseline				
LS Mean (SE)	x.xx (x.xxx)	x.xx (x.xxx)	x.xx (x.xxx)	x.xx (x.xxx)
(95% CI for LS Mean)	(x.xx, x.xx)	(x.xx, x.xx)	(x.xx, x.xx)	(x.xx, x.xx)
p-value (LS Mean = 0)	x.xxx	x.xxx	x.xxx	x.xxx
LS Mean Difference from Placebo (SE)	x.xx (x.xxx)	x.xx (x.xxx)	x.xx (x.xxx)	x.xx (x.xxx)
(95% CI for Mean Difference from Placebo)	(x.xx, x.xx)	(x.xx, x.xx)	(x.xx, x.xx)	(x.xx, x.xx)
p-value (LS Mean = Placebo LS Mean)	x.xxx	x.xxx	x.xxx	x.xxx

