Note: ANCOVA = analysis of covariance, CI = confidence interval, LS = least-squares, SE = standard error, WOMAC = West Ontario and McMasters Universities Osteoarthritis Index. Treatment arms: HP-5000-[REDACTED] topical patch, HP-5000-[REDACTED] topical patch, and Placebo.

[1] Estimates are from an analysis of covariance model with change from baseline as the dependent variable. Terms for treatment, and baseline WOMAC Pain Score as covariates are included. The restricted maximum likelihood (REML) approach for estimation is used.

SOURCE: Listings xx.x.x, xx.x.x

T:\Noven\HP-5000-US-05\...\xxxxxx.sas run on DDMMYY at HH:MM for data extracted on DDMMYY, on SAS v9.4

{Programming Note: Repeat above layout for Week 2, and Week 4}

Statistical Analysis Plan,
Sponsor Noven Pharmaceuticals, Inc.
Protocol Number HP-5000-US-05
[REDACTED]

Table 14.2.1.5.1

MMRM Analysis of WOMAC Pain Score, Multiple Imputation by Study Visit, Discontinuation as Intercurrent Event
Full Analysis Set

{Programming Note: Repeat table 14.2.1.2.3 using MI imputed records for analyses. Add footnote referencing Section 7.1.1 implementation for MI}

Table 14.2.1.5.2

MMRM Analysis of WOMAC Pain Score, Multiple Imputation by Study Visit, Rescue Medication as Intercurrent Event
Full Analysis Set

{Programming Note: Repeat table 14.2.1.2.3 using MI imputed records for analyses. Add footnote referencing Section 7.1.1 implementation for MI}

Table 14.2.1.6.1

MMRM Analysis of WOMAC Pain Score, Pattern-Mixture Model by Study Visit, Discontinuation as Intercurrent Event
Full Analysis Set

{Programming Note: Repeat table 14.2.1.2.3 using PMM imputed records for analyses. Add footnote referencing Section 7.1.1 implementation for PMM}

Table 14.2.1.6.2

MMRM Analysis of WOMAC Pain Score, Pattern-Mixture Model by Study Visit, Rescue Medication as Intercurrent Event
Full Analysis Set

{Programming Note: Repeat table 14.2.1.2.3 using PMM imputed records for analyses. Add footnote referencing Section 7.1.1 implementation for PMM}

Statistical Analysis Plan,
 Sponsor Noven Pharmaceuticals, Inc.
 Protocol Number HP-5000-US-05
 [REDACTED]

Noven Pharmaceuticals, Inc.
 Protocol HP-5000-US-05

Page 1 of x
 FINAL

Table 14.2.1.7
 Responder Analysis of WOMAC Pain Score by Study Visit
 Full Analysis Set

Visit/Category Statistics [1]	HP-5000-[REDACTED] (N=xx) n (%)	HP-5000-[REDACTED] (N=xx) n (%)	Overall HP-5000 (N=xx) n (%)	Placebo (N=xx) n (%)
Week 1				
n	xx	xx	xx	xx
5% Improvement				

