Mean (95% CI)	xx.xx (x.xx, x.xx)	xx.xx (x.xx, x.xx)	xx.xx (x.xx, x.xx)
Standard Deviation	xx.xxx	xx.xxx	xx.xxx
Median	xx.xx	xx.xx	xx.xx
Minimum, Maximum	xx.x, xx.x	xx.x, xx.x	xx.x, xx.x
Week 1 Change from Baseline			
n	xx	xx	xx
Mean (95% CI)	xx.xx (x.xx, x.xx)	xx.xx (x.xx, x.xx)	xx.xx (x.xx, x.xx)
Standard Deviation	xx.xxx	xx.xxx	xx.xxx
Median	xx.xx	xx.xx	xx.xx
Minimum, Maximum	xx.x, xx.x	xx.x, xx.x	xx.x, xx.x

Note: CI = confidence interval, NRS = Numeric Rating Scale. Treatment arms: HP-5000-[REDACTED] topical patch, HP-5000-[REDACTED] topical patch, and Placebo.

SOURCE: Listings xx.x.x, xx.x.x

T:\Noven\HP-5000-US-05\...\xxxxxx.sas run on DDMMYYYY at HH:MM for data extracted on DDMMYYYY, on SAS v9.4

{Programming Note: Continue for all applicable visits collected per protocol, and also repeat for Non-Target Knee}

Statistical Analysis Plan,
 Sponsor Noven Pharmaceuticals, Inc.
 Protocol Number HP-5000-US-05
 [REDACTED]

Noven Pharmaceuticals, Inc.
 Protocol HP-5000-US-05

Page 1 of x
 FINAL

Table 14.2.7.2
 MMRM Analysis of Pain Intensity Assessed on an 11-Point Numeric Rating Scale (NRS) by Study Visit
 Full Analysis Set

Parameter	HP-5000-[REDACTED] (N=xx)	HP-5000-[REDACTED] (N=xx)	Overall HP-5000 (N=xx)	Placebo (N=xx)
Visit/Category				
Statistics [1]				
Target Knee				
Week 1 Change from Baseline				
LS Mean (SE)	x.xx (x.xxx)	x.xx (x.xxx)	x.xx (x.xxx)	x.xx (x.xxx)
(95% CI for LS Mean)	(x.xx, x.xx)	(x.xx, x.xx)	(x.xx, x.xx)	(x.xx, x.xx)
p-value (LS Mean = 0)	x.xxx	x.xxx	x.xxx	x.xxx
LS Mean Difference from Placebo (SE)	x.xx (x.xxx)	x.xx (x.xxx)	x.xx (x.xxx)	x.xx (x.xxx)
(95% CI for Mean Difference from Placebo)	(x.xx, x.xx)	(x.xx, x.xx)	(x.xx, x.xx)	(x.xx, x.xx)
p-value (LS Mean = Placebo LS Mean)	x.xxx	x.xxx	x.xxx	x.xxx

<< Repeat for all study visits and CFB>>

Note: Analysis is based on the actual treatment received. CI = confidence interval, LS = least-squares, MMRM = repeated measures mixed model, SE = standard error, WOMAC = West Ontario and McMasters Universities Osteoarthritis Index. Treatment arms: HP-5000-[REDACTED] topical patch, HP-5000-[REDACTED] topical patch, and Placebo.

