	Week 4	DDMMYY/HH:MM	No	xxxxxxxxxxxxxx			

Note: Treatment arms: HP-5000-[REDACTED] topical patch, HP-5000-[REDACTED] topical patch, and Placebo.

T:\Noven\HP-5000-US-05\...\xxxxxx.sas run on DDMMYY at HH:MM for data extracted on DDMMYY, on SAS v9.4

Statistical Analysis Plan,
 Sponsor Noven Pharmaceuticals, Inc.
 Protocol Number HP-5000-US-05
 [REDACTED]

Noven Pharmaceuticals, Inc.
 Protocol HP-5000-US-05

Page 1 of x
 FINAL

Listing 16.2.6.1.1
 WOMAC Items
 Full Analysis Set

Actual Treatment: XXXXXX

Subject ID	Date	Visit/ Assessment		Pain [1]		Stiffness [2]		Physical Function [3]																
		1	2	3	4	5	1	2	1	2	3	4	5	6	7	8	9	10	11	12	13	14	15	16
XXXXX	Baseline/ DDMMYYYY	x	x	x	x	x	x	x	x	x	x	x	x	x	x	x	x	x	x	x	x	x	x	x
	Week 1/ DDMMYYYY	x	x	x	x	x	x	x	x	x	x	x	x	x	x	x	x	x	x	x	x	x	x	x
	Week 2/ DDMMYYYY	x	x	x	x	x	x	x	x	x	x	x	x	x	x	x	x	x	x	x	x	x	x	x
	Week 4/ DDMMYYYY	x	x	x	x	x	x	x	x	x	x	x	x	x	x	x	x	x	x	x	x	x	x	x

Note: Individual WOMAC scores are evaluated based on a likert scale and range from 0 = None, 1 = Mild, 2 = Moderate, 3 = Severe, 4 = Extremely. WOMAC = West Ontario and McMasters Universities Osteoarthritis Index. Treatment arms: HP-5000-[REDACTED] topical patch, HP-5000-[REDACTED] topical patch, and Placebo..

[1] 1. Walking, 2. Stair Climbing, 3. Nocturnal, 4. Rest, 5. Weight bearing.

[2] 1. Morning stiffness, 2. Stiffness occurring later in the day.

[3] 1. Descending stairs, 2. Ascending Stairs, 3. Rising from sitting, 4. Standing, 5. Bending to floor, 6. Walking on flat surface, 7. Getting in/out of car, 8. Going shopping, 9. Putting on socks, 10. Lying in bed, 11. Taking off socks, 12. Rising from bed, 13. Getting in/out of bath, 14. Sitting, 15. Getting on/off toilet, 16. Heavy domestic duties, 17. Light domestic duties.

T:\Noven\HP-5000-US-05\...\xxxxxx.sas run on DDMMYYYY at HH:MM for data extracted on DDMMYYYY, on SAS v9.4

Statistical Analysis Plan,
 Sponsor Noven Pharmaceuticals, Inc.
 Protocol Number HP-5000-US-05
 [REDACTED]

Noven Pharmaceuticals, Inc.
 Protocol HP-5000-US-05

Page 1 of x
 FINAL

Listing 16.2.6.1.2
 WOMAC Scores
 Full Analysis Set

Actual Treatment: XXXXXX

Subject ID	Visit	Assessment Date	Pain Score [1]	Stiffness Score [2]	Physical Function Score [3]	Composite Score [4]
XXXXX	Baseline	DDMMYY	xx	xx	xx	xx
	Week 1	DDMMYY	xx	xx	xx	xx
	Week 2	DDMMYY	xx	xx	xx	xx
	Week 4	DDMMYY	xx	xx	xx	xx
XXXXX	Baseline	DDMMYY	xx	xx	xx	xx
	Week 1	DDMMYY	xx	xx	xx	xx
	Week 2	DDMMYY	xx	xx	xx	xx
	Week 4	DDMMYY	xx	xx	xx	xx

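### The SAP analyses the primary efficacy set (FAS) by treatment received, against the protocol's FAS definition and the SAP's own as-randomised estimand

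*SAP*

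**What the plan says.** SAP 7 makes the FAS the primary efficacy population. SAP 5 gives its grouping rule: "The FAS will be used as the primary set for analysis of efficacy endpoints based on treatment actually received".

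The current protocol, in the synopsis and in 13.3, says: "The FAS will be used as the primary set for analysis of efficacy endpoints based on randomized treatment assignment". The last paragraph of 13.3 then covers a subject who is randomised incorrectly or given the wrong drug: "analyses of the ITT population will be based on the assigned treatment whereas all other analyses will be based on the actual treatment". The FAS is not the ITT set, so this paragraph reverses the FAS definition above it.

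SAP 7.1 states the primary estimand as a difference in change in "WOMAC pain score in all subjects as randomized", assuming that subjects stay on their randomised treatment. SAP 9 declares no changes from the planned analysis.

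The shells in SAP 14.2 and 14.3 are mixed:
- The MMRM shell for the ITT set, Table 14.2.1.2.3, carries "Note: Assigned/planned treatment groups are presented".
- The FAS shell for the NRS MMRM, Table 14.2.7.2, carries "Note: Analysis is based on the actual treatment received". The FAS footnote in Table 14.1.1 says the same.
- The FAS listings are headed "Actual Treatment: XXXXXX".
- Table 14.2.1.2.1, the primary Week 4 analysis, states no grouping.

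**The concern.** The primary comparison owes its validity to randomisation. Grouping by treatment received moves any misallocated subject out of the randomised arm, so the contrast is no longer the one that randomisation protects, nor the one that the estimand names. The SAP makes this change from the protocol's FAS definition without declaring it.

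The shells would let tables differ in grouping without anyone having decided that they should. If the imputation tables follow assignment while the primary table follows treatment received, they differ in two respects, and the sensitivity comparison no longer isolates the missing-data assumption.

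The received-treatment rule is also incomplete. Study drug is dispensed at Baseline, Visit 3 and Visit 4 (protocol 10.1.2 and 10.1.3), in kits that last to the next visit (protocol 9.4). The SAP does not say which arm a subject received if one of three kits is wrong. Left open, that choice could be made after unblinding.

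**Working it through.** **Comparing the texts.** The plan gives no figure on this point to reproduce. The rules for the FAS are:

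| Place | Grouping of the FAS |
|---|---|
| Protocol synopsis, FAS definition | randomised |
| Protocol 13.3, FAS definition | randomised |
| Protocol 13.3, closing paragraph | actual, after an error |
| SAP 5 | actual |
| SAP 7.1 estimand | as randomised |
| SAP Table 14.1.1, FAS footnote | actual |
| SAP Table 14.2.1.2.1 (primary) | not stated |
| SAP Table 14.2.7.2 (NRS) | actual |
| SAP FAS listing headers | actual |

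Eight further FAS tables are told to repeat ITT Table 14.2.1.2.3, which carries the assigned-treatment note. They are the four imputation tables 14.2.1.5.1, 14.2.1.5.2, 14.2.1.6.1 and 14.2.1.6.2 (for the first, "Programming Note: Repeat table 14.2.1.2.3 using MI imputed records for analyses"), then stiffness (14.2.2.2), function (14.2.3.2), composite (14.2.4.2) and PGA (14.2.5.2).

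Four of the six top-line tables in SAP 13.1 are MMRM tables. Read literally, pain is silent and so falls under SAP 5 (actual), stiffness and function inherit assigned, and NRS says actual.

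**Size, as an illustration.** The planned sizes, 75 per active arm and 150 on placebo, are from protocol 13.2. The number of errors k and the 1 SD deviation are assumptions. Suppose there is no true effect and k active-assigned subjects, each 1 SD from the arm mean in the same direction, are regrouped to placebo. With the assigned-arm means held equal:

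- shift in the contrast = k/(75 − k) + k/(150 + k), in SD units
- standard error = √[1/(75 − k) + 1/(150 + k)]

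| k | Shift (SD) | SE (SD) | Shift/SE | Two-sided rejection at nominal 5% |
|---|---|---|---|---|
| 1 | 1/74 + 1/151 = 0.0201 | 0.1419 | 0.14 | 5.23% |
| 2 | 2/73 + 2/152 = 0.0406 | 0.1424 | 0.28 | 5.93% |
| 3 | 3/72 + 3/153 = 0.0613 | 0.1429 | 0.43 | 7.11% |

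The last column is the rejection rate of a two-sample t-test whose non-centrality is the ratio shown. With deviations of 0.5 SD and k = 3 it is 5.52%. If errors are unrelated to prognosis, the expected shift under no effect is zero.

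**The other direction.** Grouping by assignment dilutes a real effect. The effect size is redacted in the current protocol; 0.32 is legible only in the synopsis of an earlier protocol version. With 75 against 150 it gives 61.5% power (t-test), not the stated 67%, so it serves only as an example. If 3 of 75 active-assigned subjects wear placebo throughout, the expected effect is 0.32 × (1 − 3/75) = 0.307 and power falls from 61.5% to 58.0%.

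**The case against.** The strongest reply has four parts.

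- **The SAP follows a protocol rule.** The closing paragraph of 13.3 addresses exactly the cases where grouping matters. This stands as an account of where the conflict began, but it leaves the protocol with two opposite rules in one section. Of these, only randomised assignment agrees with the FAS definition, the synopsis and the estimand.
- **The estimand is hypothetical.** It assumes that everyone stays on randomised treatment, so for a misdosed subject neither grouping matches it fully, and the dilution shown above is itself a departure. That is fair. It does not undo the choice of randomised groups as the groups to compare.
- **An as-assigned analysis is already planned.** Table 14.2.1.2.3 runs the MMRM in the ITT set. Because that model needs a baseline and a post-baseline score, it would differ from an as-randomised FAS analysis only for subjects with WOMAC data but no patch applied. Any effect of grouping would therefore be visible. But the table is supportive and is not among the top-line tables.
- **Repeating a table may mean layout only.** This is plausible, since the inherited footnote also names baseline WOMAC pain as covariate, which cannot stand for PGA. It weakens the point about the shells and leaves SAP 5 unchanged.

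Errors should also be rare: allocation is central and the trial is double-blind, and SAP 5 itself calls assignment errors unlikely (for the safety and PK sets). An adverse run of prognostically extreme errors is a constructed case.

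**Conclusion.** The concern holds and should be fixed. SAP 5 sets a grouping for the primary efficacy set that contradicts the protocol's FAS definition and the SAP's estimand. The root is an internal contradiction in protocol 13.3, and the shells leave the grouping unclear.

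The effect on results is nil if no subject is misrandomised or misdosed, and the documents give no rate from which to expect otherwise. In the assumed adverse case of one to three subjects, the error rate moves by about 0.2 to 2.1 percentage points. The case for correction rests less on that size than on the need to fix, before unblinding, which groups the primary analysis compares.

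**What to change.** 1. In SAP 5, state that the FAS is analysed by randomised treatment assignment.
2. Make every FAS table footnote and FAS listing header agree, including the silent primary shell, the NRS shell, the FAS footnote in Table 14.1.1 and the eight tables that repeat the ITT shell.
3. Amend the closing paragraph of protocol 13.3 so that ITT and FAS use assigned treatment, and the safety and PK sets use actual treatment.
4. For the safety and PK sets, define treatment received for a subject given kits from more than one arm.

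Items 1 and 2 settle the efficacy analysis and cost one phrase plus footnote and header edits. Item 3 is one sentence but needs the amendment procedure of protocol 14.6 and 15.3; item 4 is one added rule. No data collection, sample size or trial procedure changes. The price is the modest dilution shown above if dosing errors occur.
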